Study Protocol, Statistical Analysis Plan and Informed Consent Form

Efficacy of percutaneous laser disc decompression versus
epidural steroid and local anesthetic injection by
transforaminal approach in the treatment of lumbar radicular
pain

26.09.2022.

Study Protocol

The research is designed as a randomized controlled trial, and will be conducted at the Clinic for Anesthesiology, Reanimatology and Intensive Care Medicine of the Osijek Clinical Hospital Center after obtaining the approval of the Ethics Committee. All patients will receive a written informed consent describing the procedure to be performed, and the procedure will also be explained to them orally. After signing the informed consent, patients will be divided into 2 groups depending on whether there is diascorradicular contact or not, and then within each group depending on the method (ESI or PLDD).

Subjects will be between the ages of 18 and 65 who agree to participate in the study, which they confirm by signing the informed consent, have unilateral lumbar radicular pain that does not respond to conservative treatment, disc herniation at one level, MR verified disc herniation, pain intensity measured with the VAS scale >5 . The obtained data will be statistically processed.

Exclusion criteria will be: patients younger than 18 and older than 65 years, refusal of the patient to participate in the research, central stenosis of the lumbar canal, lumbar radicular pain caused by causes other than intervertebral disc herniation, pregnancy, allergy to steroids, local anesthetics, fentanyl, midazolam and contrast agent, positive history of prolonged bleeding, local or systemic infection, previous lumbar spine surgery, opioid abuse, proven inflammatory rheumatic disease and inflammatory bowel disease in the active phase, and other acute infections.

To observe a mean effect in the difference of numerical variables between four independent groups of subjects, with a significance level of 0.05 and a power of 0.80, the minimum required sample size is 116 subjects (29 subjects per group) (calculation made using the program G*Power version 3.1.2, Franz Faul, University of Kiel, Germany).

Patients will have 4 measurements. The first measurement will be before the procedure, the second measurement will be at the follow-up examination after one month, the third measurement at the follow-up examination 3 months after the procedure, and the fourth measurement at the follow-up examination 6 months after the procedure. Control MR of the LS spine will be done 6 months after the procedure.

The VAS scale (Visual Analogue Scale) will be used to assess pain intensity. The questionnaires will be SF-36 (Short form health survey-36), Oswestry Disability Questionnaire Index (ODI), Pain Detect, Hospital Anxiety and Depression Scale (HADS), and the Pittsburgh Sleep Quality Index (PSQI).

From the clinical examinations, the Lasegue test, the toe-heel test and the flexion test will be performed. Among the laboratory tests, the level of interleukin 6 (IL-6), C-reactive protein (CRP), leukocyte count and differential blood count (DKS) will be determined. The mentioned parameters will be analyzed in three visits: before the procedure, one month after the procedure and after 6 months.

Statistical Analysis Plan

Categorical data will be represented by absolute and relative frequencies. Numerical data will be described by the arithmetic mean and standard deviation in the case of distributions that follow the normal, and in other cases by the median and the limits of the interquartile range. Differences in categorical variables will be tested with the χ^2 test, and if necessary, with Fisher's exact test. The normality of the distribution of numerical variables will be tested with the Shapiro-Wilk test. Differences of normally distributed numerical variables between two independent groups will be tested with Student's t test, and in case of deviation from normal distribution with Mann-Whitney U test. Differences of normally distributed numerical variables in case of 3 or more independent groups will be tested by analysis of variance (ANOVA), or Kruskal-Wallis test (Post hoc Conover). Differences of normally distributed numerical variables between 4 measurements will be tested by analysis of variance for repeated measurements, and in case of deviation from normal distribution by Friedman test. The association of normally distributed numerical variables will be assessed by Pearson's correlation coefficient r , and in case of deviation from normal distribution by Spearman's correlation coefficient ρ (rho). All P values will be two-sided. The significance level will be set at $\alpha=0.05$. For statistical analysis, the statistical program MedCalc Statistical Software version 19.1.7 (MedCalc Software Ltd, Ostend, Belgium; <https://www.medcalc.org>; 2020) and SPSS (version 16.0, SPSS Inc., Chicago, IL, NOW).

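### Group comparisons of numerical outcomes leave the collected baseline value unused, no pooled PLDD-ESI comparison accounts for discoradicular contact, and the four-measurement analysis states no group term

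*Combined protocol and SAP*

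**What the plan says.** The Study Protocol section says patients are "divided into 2 groups depending on whether there is diascorradicular contact or not, and then within each group depending on the method" (ESI or PLDD). This gives four cells, sized at 29 each, 116 in all. Each patient has four measurements: "The first measurement will be before the procedure, the second measurement will be at the follow-up examination after one month", followed by visits at 3 and 6 months. For the laboratory tests, "The mentioned parameters will be analyzed in three visits: before the procedure, one month after the procedure and after 6 months". A baseline value therefore exists for VAS, the questionnaires and the laboratory values.

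The Statistical Analysis Plan section lists these tests for numerical variables:

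- Two groups: differences "between two independent groups will be tested with Student's t test, and in case of deviation from normal distribution with Mann-Whitney U test".
- More groups: differences "in case of 3 or more independent groups will be tested by analysis of variance (ANOVA), or Kruskal-Wallis test (Post hoc Conover").
- Over time: "Differences of normally distributed numerical variables between 4 measurements will be tested by analysis of variance for repeated measurements", with the Friedman test if normality fails.

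No covariate, stratified test, treatment term or treatment-by-time term appears. The Pearson and Spearman coefficients describe association and adjust nothing. The section does not say whether follow-up scores or changes from baseline are compared, or at which visit.

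**The concern.** There are two separate gaps.

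**Precision.** The trial asks how PLDD compares with ESI. Two variables that may explain part of the outcome, its own baseline value and the contact group, are on file before treatment. A comparison that ignores them has a wider confidence interval than the same patients could give. The error rate is not at stake.

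**The question answered.** A repeated-measures ANOVA or Friedman test with no group term asks whether scores change over the visits. Patients in both arms may improve, and such a test would then be significant without saying anything about one method against the other. Here the written analysis does not address the trial's question, whatever its precision.

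**Working it through.** **Inputs from the documents.** Two-sided alpha 0.05; target power 0.80; four groups of 29; four measurements; VAS above 5 at entry. Pooling over contact gives 2 × 29 = 58 per method.

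**Assumptions, because the documents give no figures.** PLDD-ESI difference d = 0.5 SD; baseline to follow-up correlation r = 0 to 0.5; Cohen's f = 0.25 as the meaning of the protocol's mean effect; no dropout.

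**1. The plan's own 116.**

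- One-way ANOVA, four groups, f = 0.25: power at 116 is 0.590, and 180 patients would be needed. To need only 116, f would have to be 0.312.
- Between-group factor over m = 4 measurements with an assumed correlation of 0.5: noncentrality = f² × N × m / (1 + (m − 1) × 0.5) = 0.0625 × 116 × 4 / 2.5 = 11.6. Power is 0.812 at 116 and 0.796 at 112, so 116 is the smallest equal-cell total.

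The figure thus fits a calculation with a group factor in the repeated-measures analysis. The SAP does not write that factor down.

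**2. Precision of PLDD vs ESI at one visit.** ANCOVA on the follow-up score has variance 1 − r² relative to the unadjusted comparison, so the standardised effect becomes d / √(1 − r²). Degrees of freedom fall from 114 to 112. Power is from the noncentral t.

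| Analysis | Power | 95% CI half-width (SD) | Unadjusted patients equivalent, 116/(1 − r²) |
|---|---|---|---|
| t test | 0.761 | 0.37 | 116 |
| ANCOVA, r = 0 | 0.761 | 0.37 | 116 |
| ANCOVA, r = 0.2 | 0.778 | 0.36 | 121 |
| ANCOVA, r = 0.3 | 0.799 | 0.35 | 127 |
| ANCOVA, r = 0.5 | 0.869 | 0.32 | 155 |

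Allowing for chance baseline imbalance (mean variance inflation 1.009) lowers each ANCOVA power by 0.003 to 0.004. At r = 0 it is 0.757, which is the whole cost of an uninformative baseline. In simulation with normal errors, r = 0 and no contact effect, power was 0.759 for the t test, 0.753 for ANCOVA and 0.743 for ANCOVA with HC3 standard errors.

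**3. If change scores were meant.** With k = baseline SD / follow-up SD, their relative variance is 1 + k² − 2rk. The excess over ANCOVA is (1 + k² − 2rk) − (1 − r²) = (k − r)². A change score can match ANCOVA when k = r, but its variance is never smaller.

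**4. VAS.** Entry requires "pain intensity measured with the VAS scale >5". Assume normal scores with SD 2 and mean 5 to 7 before selection, kept if above 5 and at most 10. In-trial k is then 0.58 to 0.70, and the in-trial correlation is r × k. An r of 0.3 becomes about 0.17 to 0.20, and 0.5 becomes 0.31 to 0.35. Power is about 0.77 to 0.81 against 0.76.

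**5. Contact.** At a difference of 0.525 SD, where the unadjusted test has power 0.80, adjusting for contact alone gives 0.808, 0.820 and 0.840 if contact explains 2%, 5% and 10% of the variance. With allocation balanced within contact groups, the type I error of the pooled t test is 0.050, 0.039 and 0.019 when contact explains 0%, 10% and 30%. The test is valid, and conservative when contact matters.

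**6. Skewed outcomes.** Simulation with four cells of 29, lognormal outcome (log SD 1), effect 0.5 log-SD, log-scale r = 0 to 0.5:

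| Analysis | Power |
|---|---|
| Mann-Whitney, as planned | 0.73-0.75 |
| Raw-scale ANCOVA, robust SE | 0.56-0.62 |
| ANCOVA on the log scale | 0.76-0.87 |
| Rank ANCOVA | 0.74-0.84 |

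**7. Treatment-by-contact.** The SE is √(4/29 × (1 − r²)). The half-width is 0.74 SD unadjusted, and 0.70 and 0.64 SD at r = 0.3 and 0.5. Power for a 0.5 SD interaction is 0.27, rising to 0.29 and 0.34, so this term serves estimation and not testing.

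**The case against.** **The four-group test already handles contact.** In part this stands. If the four groups are the contact-by-method cells, ANOVA removes contact from its error term, and a post hoc pair within one contact group holds contact fixed. A reader might infer that the plan ignores contact altogether; the text does not support that. But the four-group test has 3 degrees of freedom and is not a PLDD-ESI estimate. The within-group pair is 29 vs 29 and is not named in the SAP. Neither uses baseline.

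**A group factor was probably intended in the repeated-measures ANOVA.** The sample size sentence, "To observe a mean effect in the difference of numerical variables between four independent groups of subjects", and the match at 116 point that way. One should therefore not conclude that the sponsor planned no treatment comparison over time, only that none is written. The match rests on an assumed f and correlation.

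**ANCOVA is not always better than what is planned.** This stands. For skewed data, raw-scale ANCOVA loses clearly to the Mann-Whitney test already in the plan (step 6). It would be tempting to recommend ANCOVA for every outcome at negligible cost; that does not hold.

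**The gain is small and assumed.** It is assumed, and for VAS probably modest. The questionnaires and laboratory values have no entry limit, and the loss at r = 0 is about 0.004.

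**Conclusion.** The point holds as one of precision and clarity. No stated between-group test of a numerical outcome uses the baseline value, and no pooled PLDD-ESI comparison accounts for contact. With d = 0.5 SD and 58 vs 58, this forgoes about 0.02 to 0.11 in power at r = 0.2 to 0.5 (0.778 − 0.761 and 0.869 − 0.761), and about 0.01 to 0.05 for VAS. All of these rest on assumed d and r and, for VAS, on an assumed score distribution before selection. Separately, the four-measurement analysis as written does not compare PLDD with ESI. That is a gap in the question answered, not in precision.

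A reader might infer that the planned tests are biased or exceed their 5% error rate. They do not: simulated type I error was 3.7% to 5.4% for the t test and ANCOVA with normal and exponential errors and a contact effect of 0 or 0.5 SD, and below 5% when contact explains more of the variance.

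**What to change.** 1. For outcomes expected to be roughly normal, make the PLDD-ESI comparison an ANCOVA on the follow-up score with treatment, contact group and that outcome's baseline value. A mixed model of the follow-up visits with treatment-by-visit and the same covariates is an alternative. Report the adjusted difference with its 95% CI, and name the visit for each comparison (1, 3 and 6 months; 1 and 6 months for laboratory values).
2. For outcomes expected to be skewed (for example IL-6 and CRP, which is an assumption), pre-specify adjustment on the log scale or by rank ANCOVA with the same terms. Do not replace Mann-Whitney with raw-scale ANCOVA there.
3. Report treatment-by-contact or within-contact-group estimates with CIs, so that the four-group question is kept.
4. State the group and group-by-time terms of the repeated-measures analysis, and which term is the PLDD-ESI comparison.

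The cost is SAP wording and a little more analysis. All the variables are already collected, and no patient or visit is added. If baseline proves uninformative, power falls by about 0.004, or 0.01 to 0.02 with HC3 standard errors; these figures apply to roughly normal outcomes.

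### The PLDD–ESI contrast is not named, and no listed analysis combines the two contact groups into one PLDD–ESI estimate or uses the pre-procedure value

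*Combined protocol and SAP*

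**What the plan says.** The title sets up a two-treatment question: "percutaneous laser disc decompression versus" transforaminal epidural injection. In the Study Protocol's design paragraph, "patients will be divided into 2 groups depending on whether there is diascorradicular contact or not". The division by treatment comes second: "and then within each group depending on the method (ESI or PLDD"). This is a 2 × 2 layout in which contact is a patient characteristic and only method is a treatment.

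The sample-size paragraph is written for a different question: "To observe a mean effect in the difference of numerical variables between four independent groups of subjects". It gives 116 subjects, 29 per group, at significance level 0.05 and power 0.80, with no numerical effect size.

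The Statistical Analysis Plan chooses tests by the number of groups:
- Two groups: "Differences of normally distributed numerical variables between two independent groups will be tested with" Student's t test, or Mann-Whitney if the data are not normal. The two groups are not identified.
- More groups: differences "in case of 3 or more independent groups will be tested by analysis of variance (ANOVA), or Kruskal-Wallis test (Post hoc Conover").
- Repeated-measures ANOVA or Friedman: described only for differences across the four measurements.

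PLDD, ESI and contact do not appear in the Statistical Analysis Plan as factor, stratum or covariate. A baseline is collected ("The first measurement will be before the procedure"), but no between-group analysis uses it.

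**The concern.** Four cells formed from two factors can differ because of treatment, contact or both. A single three-degree-of-freedom test does not separate these. A significant result correctly rejects equality of the four cells, but it does not say whether PLDD differs from ESI.

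The two-group and Conover tests could supply the treatment comparison, but the plan does not say whether it is made pooled, within each contact group, or both. The choice is therefore open after the data are seen. A comparison within one contact group has low power. Two such tests side by side can easily give one significant and one non-significant result when the treatment effect is the same in both, and this could be misread as a contact-specific effect.

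What is at stake is whether the trial reports one pre-stated PLDD–ESI estimate, with an interval, that uses all patients and the baseline already measured.

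**Working it through.** **Inputs from the documents.** N = 116, 29 per cell (so 58 PLDD and 58 ESI), two-sided α = 0.05. The documents give no effect size, SD, contact effect or baseline correlation. All such values below are assumptions, in units of the within-cell SD, at one time point. Power is from the noncentral F with noncentrality λ.

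**The plan's own figure.** 116 cannot be reproduced from the stated inputs, because no effect size is given. Two readings reach it:
- One-way ANOVA, four groups, λ = N f²: power is 0.80 at N = 116 when f = 0.312. At f = 0.25 it would need 180.
- Between-groups repeated measures, f = 0.25, four measurements, assumed correlation 0.5: λ = 116 × 0.25² × 4/(1 + 3 × 0.5) = 11.6, power 0.81. The smallest such N is exactly 116.

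Both are four-group tests.

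**1. Four-group ANOVA with no treatment effect and contact effect c.** Cell means are ±c/2, so λ = 116 (c/2)² = 29c², df 3 and 112.

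| c (SD) | λ | P(significant) |
|---|---|---|
| 0.3 | 2.61 | 0.235 |
| 0.5 | 7.25 | 0.590 |
| 0.8 | 18.56 | 0.958 |

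In simulation (20,000 runs) a one-df treatment contrast in the 2 × 2 model rejected in 4.9%, 5.1% and 5.1% of runs at c = 0.5, 0.8 and 1.0.

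**2. PLDD–ESI difference d = 0.5 SD in both contact groups.**
- Treatment plus contact: variance of the difference is 1/58 + 1/58 = 1/29, so λ = 29 × 0.25 = 7.25, df 1 and 113; power 0.761. Power is 0.80 at d = 0.525.
- Pooled t test ignoring contact: power 0.742, 0.711 and 0.682 for c = 0.5, 0.8 and 1.0; type I error 4.3%, 3.5% and 2.8%.
- t test within one contact group (29 v 29): λ = 14.5 × 0.25 = 3.625, df 1 and 56; power 0.465. Both significant: 0.465² = 0.216. Exactly one: 2 × 0.465 × 0.535 = 0.498. With no effect, at least one: 1 − 0.95² = 0.0975.

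**3. Adding the pre-procedure value, correlation r.** λ = 7.25/(1 − r²), df 1 and 112.

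| r | λ | Power at 0.5 SD |
|---|---|---|
| 0.3 | 7.97 | 0.799 |
| 0.5 | 9.67 | 0.869 |
| 0.7 | 14.22 | 0.962 |

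At r = 0.5, power is 0.80 at d = 0.454.

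**4. Where the average effect does worse: 0.8 SD in one contact group, 0 in the other.**
- Average effect 0.4: λ = 29 × 0.16 = 4.64; power 0.570.
- t test within the benefiting group: λ = 14.5 × 0.64 = 9.28; power 0.849.
- Four-group test, other three cells equal: λ = 29 (0.6² + 3 × 0.2²) = 13.92; power 0.88.
- Four-group test, no contact main effect (cells +0.4, −0.4, 0, 0): λ = 29 × 0.32 = 9.28; power 0.71.

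**5. Interaction.** λ = (29/4)D², df 1 and 112. For a difference of D = 0.5 SD between contact groups, λ = 1.81 and power is 0.27. D = 1.05 is needed for 0.80.

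**The case against.** **Some listed tests do account for contact.** A t test, Mann-Whitney test or Conover pair comparing PLDD with ESI within a contact group holds contact fixed, and the design paragraph points that way. This stands: a reader might infer that the plan has no contact-aware comparison at all, and the documents do not support that. The gap is that no contrast is named and none combines the two groups. Conover pairs also use the ranks of all 116 patients, so the 0.46 applies to the t test within one group.

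**Contact adjustment alone gains little.** This also stands. At 0.5 SD the pooled t test has 0.74 against 0.76 when the contact effect is 0.5 SD, and it errs on the conservative side. Most of the gain comes from the baseline value. That gain rests on assumed correlations, and it may be smaller for VAS because entry requires "pain intensity measured with the VAS scale >5", which restricts the baseline range.

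**A contact-specific effect may be the real interest.** The design divides on contact first. If benefit is confined to one contact group, the average effect is the weaker test (step 4). This is a real cost, and the reason to report contact-group estimates too.

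**Misuse is not stated.** Nothing says that the four-group P value, or a pair comparing PLDD in one contact group with ESI in the other, will be presented as efficacy. That is correct. The point is that the plan leaves this open, not that it intends it.

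**Conclusion.** The concern holds for numerical outcomes. The sample size and the four-group test address equality of four cells. The treatment comparison in the title is left to generic tests with no named contrast, no estimate combining the contact groups and no use of baseline. With no treatment effect, the four-group ANOVA would be significant with probability 0.24, 0.59 or 0.96 for contact effects of 0.3, 0.5 or 0.8 SD. At 0.5 SD, moving from a treatment-plus-contact model to one that adds baseline raises power from 0.76 to between 0.80 and 0.96 for r from 0.3 to 0.7. All effect sizes and correlations are assumed, at one time point, with 29 analysed per cell.

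A reader might infer that 116 is wrong or too small. The documents do not support this. The figure is reachable under at least two sets of assumptions. If the one-way reading is right, a treatment difference of 2 × 0.312 = 0.624 SD has power 0.91 in the one-df test. The fault is that the size is stated for a different question.

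This should be corrected before analysis. The data to be collected can answer the title question; the plan does not yet say how.

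**What to change.** In the Statistical Analysis Plan, for each numerical outcome at each follow-up:
- Estimate the PLDD–ESI difference with 95% CI from a linear model with treatment, contact (yes/no) and the pre-procedure value of that outcome.
- Where ranks are used, use a contact-stratified (van Elteren) test with tie correction, since questionnaire scores will tie.
- Report the treatment-by-contact interaction and the PLDD–ESI difference with CI in each contact group. Say that the interaction test is weak, so a non-significant result does not show equal effects.
- State that the four-group P value is not evidence of efficacy.

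Restate the sample-size paragraph for the PLDD–ESI contrast, giving the assumed difference, SD, time point and baseline correlation. At one time point, 116 gives 0.80 power for 0.525 SD unadjusted, or about 0.45 SD with an assumed correlation of 0.5.

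The cost is rewording. Patients, visits, measurements and enrolment are unchanged. The statistical price is lower power for the average effect when benefit is confined to one contact group, for which the contact-group estimates are the safeguard.

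### The across-visit tests use only patients with every measurement, so a missed visit discards values already recorded and the across-visit result describes completers

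*Combined protocol and SAP*

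**What the plan says.** The Study Protocol, in its paragraph on measurements, states "Patients will have 4 measurements": before the procedure, at one and three months, and "the fourth measurement at the follow-up examination 6 months after the procedure". Pain is one of the outcomes: "The VAS scale (Visual Analogue Scale) will be used to assess pain intensity". Laboratory values follow a shorter schedule: "The mentioned parameters will be analyzed in three visits: before the procedure, one month after the procedure and after 6 months". It is not clear whether that sentence also covers the clinical tests named just before it.

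The Statistical Analysis Plan gives one rule for change over time: differences "between 4 measurements will be tested by analysis of variance for repeated measurements, and in case of deviation from normal distribution by Friedman test". Differences between groups have their own rule, which is the t test or Mann-Whitney for two groups and ANOVA or Kruskal-Wallis for three or more.

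The sample-size paragraph of the Study Protocol says "the minimum required sample size is 116 subjects (29 subjects per group", "with a significance level of 0.05 and a power of 0.80". It states no dropout allowance. Nowhere do the documents mention missing data, imputation, withdrawals, an analysis set or a mixed model.

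**The concern.** Repeated-measures ANOVA and the Friedman test both work on one full row per patient. With nothing planned for gaps, a patient seen at baseline and month 1 who misses months 3 and 6 drops out of the across-visit analysis altogether, including the two values already recorded. The month-1 group comparison still uses that patient. The same outcome is then reported on two sets of patients, and the longitudinal set is selected on having finished follow-up.

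Two things are at stake. Recorded data are lost whatever the reason for the missed visit. In addition, if attendance depends on pain, the course over six months is described for an unrepresentative subset. That dependence is plausible in patients who enter with VAS above 5 after failed conservative treatment.

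**Working it through.** **Do the named tests need complete rows?** A trial run with 29 patients, four measurements and one missed visit in one patient gave the expected answer. A standard repeated-measures ANOVA routine rejected the data as unbalanced, and a standard Friedman routine returned no result. The patient must be removed or imputed, and no imputation is planned.

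**The plan's 116.** The effect size is not given as a number. A one-way ANOVA with four groups and f = 0.25 needs 180, and 116 would need f of about 0.312. A repeated-measures ANOVA (between factors, 4 groups, m = 4 measurements) with assumed f = 0.25 and correlation ρ = 0.5 reproduces 116:

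- λ = N·f²·m / (1 + (m − 1)ρ) = 116 × 0.0625 × 4 / 2.5 = 11.6, with 3 and 112 degrees of freedom, gives power 0.81.
- 112 patients give 0.796.

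On that reading, 116 counts patients with all four measurements and has no reserve beyond rounding.

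**How many patients are complete?** Assumption: each of the 3 follow-up visits is missed independently with probability q. The complete count is 116(1 − q)³, and the count seen at any one visit is 116(1 − q).

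| q | Complete | Seen at each visit |
|---|---|---|
| 5% | 116 × 0.857 = 99 | 110 |
| 8% | 116 × 0.779 = 90 | 107 |
| 10% | 116 × 0.729 = 85 | 104 |

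If instead 10% of patients in total are incomplete, 116 × 0.90 = 104 remain. Laboratory values have two follow-ups, so 116 × 0.95² = 105 and 116 × 0.90² = 94 would be complete.

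**How many recorded values are discarded?** This is 116[1 + 3(1 − q)] − 4 × 116(1 − q)³.

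- q = 5%: 446.6 − 397.8, about 49 values.
- q = 10%: 429.2 − 338.3, about 91 values.

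**Power, if 116 was calculated as above.** Complete cases give about 0.74 (q = 5%) and 0.66 (q = 10%). A likelihood analysis of all available visits (constant group shift, compound symmetry, ρ = 0.5) keeps an effective N of about 115 and 114, with power of about 0.81 and 0.80.

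**Bias if worse pain leads to leaving.** All inputs are assumed. Baseline VAS is 7 (SD 1.2), and follow-up means are 4.5 in one arm and 3.5 in the other (SD 2). The correlation is 0.6 between follow-ups and 0.3 with baseline. Patients with VAS 6 or more at month 1 or month 3 then leave with probability 0.5. In large simulated arms, about 80% and 90% complete.

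| | Worse arm | Better arm |
|---|---|---|
| True improvement, every follow-up | 2.50 | 3.50 |
| Completers, month 6 | 6.89 − 4.13 = 2.76 | 6.94 − 3.29 = 3.65 |
| Completers, month 1 | 6.89 − 4.00 = 2.89 | 6.94 − 3.22 = 3.72 |
| Likelihood, all visits, month 6 | 2.50 | 3.50 |

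The month-1 row is due entirely to deletion, because in this scenario every month-1 value was recorded. At month 6 the completers are exactly the attendees, so the distortion there comes from absence itself. The VAS difference between arms among month-6 attendees is 4.13 − 3.29 = 0.84 against a true 1.0.

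A separate simulation with dropout unrelated to pain showed no bias, only fewer patients.

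**The case against.** **Between-arm effect.** A reader might infer that deleting incomplete patients shrinks the PLDD-ESI difference at month 1. In the scenario above, completers do show 3.72 − 2.89 = 0.83 instead of 1.0. The documents do not support that inference. The SAP assigns the quoted tests to change between measurements and tests group differences separately. Everyone attends month 1 in the scenario, so the group test there gives 4.5 − 3.5 = 1.0. The across-visit rule states no group or group-by-visit term, although it does not exclude one.

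**Direction.** A reader might also infer that completers always look better. That holds only if patients in worse pain leave. If recovered patients skip visits, the sign reverses.

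**Consequence for the test itself.** Under the assumed inputs the SD of change is √(1.2² + 2² − 2 × 0.3 × 1.2 × 2) = 2.0. With 29 patients the standard error is 2.0/√29 = 0.37, and an improvement of 2.5 is about 6.7 standard errors. A bias of 0.15 to 0.39 changes the described course, not whether change is detected. This stands.

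**Numbers.** Independent misses are a pessimistic layout, and 116 is called a minimum with no enrolment cap, so fewer than 29 complete patients per group is possible but not certain. This stands too. The power figures also depend on f and ρ, which the documents do not give.

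The mechanism is untouched by these points: the named tests need full rows, and the plan offers nothing else for incomplete patients.

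**Conclusion.** The point holds for the across-visit analysis. Followed as written, the plan deletes recorded values of anyone who misses a visit, and the reported course over time is that of completers. The documents do not say complete cases in words; it follows from the named tests and the absence of any other rule.

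The between-group tests are not affected by this deletion at month 1. At months 3 and 6 they rest on attendees and share the problem of absence, though not that of deletion.

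The loss of recorded values is certain once any visit is missed. How many patients are lost depends on an unstated dropout rate. The size and direction of any bias depend further on why patients are absent. The change should be made, but the trial's between-group comparisons do not fail without it.

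**What to change.** - For VAS and the questionnaire scores, replace the repeated-measures ANOVA/Friedman rule with a linear mixed model for repeated measures. Include visit, treatment, treatment-by-visit, disc-contact group and the interactions needed for the four groups, with unstructured covariance.
- Use all available measurements of all randomised patients. With baseline as one of the modelled measurements, patients who leave before month 1 still contribute.
- For the three-visit laboratory values, use the same model on a log or other suitable scale, or keep a rank-based analysis as a sensitivity check.
- Report the number analysed per visit and group.
- Keep the completer ANOVA/Friedman as a secondary analysis.

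The cost is SAP wording and some additional analysis work. SPSS, already named in the plan, has a mixed-model procedure. The model assumes that missingness is explained by observed values. This is weaker than what the completer analysis needs but is still an assumption, and it should be stated. Skewed outcomes lose the automatic switch to Friedman and so need a transformation or a sensitivity check.
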